# 4 TRIAL DESIGN

This will be an open label, randomised, controlled pilot and exploratory study which will be powered to detect superiority of the addition of acetazolamide 250mg BD by mouth (PO) in conjunction with 240mg/24 hours furosemide IVI on diuresis and chloride homeostasis compared to 240mg/24 hours IV furosemide infusion alone (standard of care) both primary endpoints with the primary aim of gathering data on the feasibility and tolerability of the intervention which will inform a larger study.

# 5 STUDY SETTING

The study will be run at a single site: Castle Hill Hospital (CHH), Cottingham, Kingston upon Hull, East Yorkshire. The site has been chosen as it is the base of the primary and chief investigators and is a tertiary cardiology centre treating patients with heart failure from across East Yorkshire and Northern Lincolnshire.

Most patients who will be invited to take part will be admitted first under the care of General Medicine at a different site ~5 miles away – Hull Royal Infirmary (HRI). Upon referral to the cardiology team at HRI patients are assessed for their clinical suitability for transfer to the specialist unit at CHH. Only patients in who the primary reason for admission is venous congestion due to heart failure are transferred to CHH which has three cardiology wards – ward 26, 28 and the cardiac monitoring unit (CMU). A patient who has heart failure due to severe anaemia or chest infection will remain at HRI under the care of the team responsible for treatment the primary problem.

Patients will be identified by daily ward rounds by the study doctors ([name]) on the acute cardiology wards (ward 26, ward 28 and the cardiac monitoring unit at CHH). They will be assessed against inclusion/exclusion criteria and introduced to the nature and purpose of the study. Each eligible participant will be informed of the aims, methods, anticipated benefits and potential hazards of the study and their right to withdraw consent at any stage, using both the patient information sheet (PIS) and verbally. Patients will have the opportunity to ask any and all questions before giving written consent. Confirmation of the approach for study participation, outcome (participation or not) and confirmation of written consent will be documented in the medical notes by the study doctor.

# 6 ELIGIBILITY CRITERIA

Inclusion criteria

# Hull University Teaching Hospitals

1) Aged >18 of any gender and able to give informed consent (All women of child bearing potential (see appendix 3 for definition) must have a negative pregnancy test regardless of contraceptive use. The only form of contraception that will be allowed during the trial is abstinence.)

2) Heart failure of any aetiology (new or established diagnosis)

3) Admitted to hospital with a primary diagnosis of peripheral oedema caused by heart failure and deemed by treating clinicians to require treatment with intravenous diuretic.

4) Deemed to require standard of care – 10mg/hr continuous furosemide infusion.

5) Patients whose medications have been discontinued for other reasons  $\geq$ 48 hours previously may be considered eligible. These medications include; sodium glucose co-transporter 2 inhibitors, thiazide or thiazide-like diuretics, high dose aspirin ( $\geq$ 500mg / day), methotrexate, lithium, Sando-K®, sodium bicarbonate, other sodium tablets, oral steroids, or sodium valproate.

#### Exclusion criteria

1) Unable to give informed written consent

2) Allergy or contraindication to carbonic anhydrase inhibitors

3) Patient thought to be at end-of-life

4) Concurrently taking thiazide (or thiazide-like) diuretic or sodium-glucose linked transporter-2 inhibitor, high dose aspirin (>500mg / day), methotrexate, lithium, or sodium valproate, oral steroids Sando-K®, oral sodium bicarbonate, or other sodium tablets

5) Severe anaemia (haemoglobin <8 g/DL); or severe infection (investigator opinion).

6) SBP <80 mmHg at randomisation

7) Serum sodium (severe hyponatraemia) <130 mmol/L at randomisation

8) Serum potassium (hypokalaemia) <3.5 mmol/L at randomisation

9) Serum chloride (severe hyperchloraemia) >110 mmol/L at randomisation

10) Severe renal dysfunction with an eGFR (estimate glomerular filtration rate) result of  $\leq$ 20 ml/min calculated by the Cockcroft-Gault formula

12) Pregnant or breast feeding, or intends to become pregnant whilst taking part in the trial

# 7 TRIAL PROCEDURES

# 7.1 Recruitment

Patients will be identified as detailed below on cardiology wards at CHH and Hull Royal Infirmary (HRI) and screened for eligibility with consent by the study team. Data on patients age, gender, and eligibility status will be recorded anonymously to help define the generalisability of the results. We estimate the recruitment period will be for 30 weeks but can be extended to 52 weeks. We aim to recruit a minimum of 40 patients with a maximum of 50 during that time frame.

# 7.1.1 Patient identification

Potentially eligible patients with HF will be identified by the treating team who will inform the study team. The study team will then approach each patient for consent to screen the medical notes

(electronic and paper) for inclusion / exclusion criteria, the approach and the outcome will be documented in the medical notes. If consent is given the study doctor will use all electronic and paper medical records alongside taking a detailed medical history from the patient to decipher whether or not a patient is eligible.

Identification of potentially eligible patients will be done by the treating team but confirmation of eligibility will be done by the study team in order to streamline the process from identification to consent and enrollment. Given the busy nature of clinical work we feel it would be too great a burden to place on the treating team that they assess each patient against all eligibility criteria and recruitment may suffer as a result.

# 7.1.2 Screening

Screening will involve detailed history from the patient alongside reviewing all electronic and medical records. All data required for screening is collected as part of routine care.

Patients who fail initial screening may subsequently become eligible for inclusion. A patient who fails initial screening will be informed of this and verbal consent obtained for re-screening at 48 hour intervals (done remotely using the electronic record), and for the treating team to inform the study team should the reason for the screen failure resolve (IE low systolic blood pressure). There is a maximum limit of three re-screens per patient however; this will be limited by the duration of in-patient stay.

# 7.2 Informed Consent

After the confirmation of eligibility and reconfirmation that the patient wishes to proceed, each potential participant will be informed of the aims, methods, nature of participation, anticipated benefits and potential hazards of the study, the alternatives to taking part and their right to withdraw consent at any stage without giving a reason and without prejudicing further treatment. The person taking consent will assume each participant to have capacity to give consent unless concerns are raised by the treating team or during the screening process (e.g. history of dementia or confusion on admission, nursing or medical concerns regarding cognition).

If concerns are raised, each participant will be assessed against the 2 stage capacity assessment defined by the Mental Capacity Act: 1) Is the patient able to make a particular decision? and 2) Is the person able to understand, retain and use information given to come to a decision and are they able to communicate this decision? If a person is deemed unable to give valid consent they are ineligible for the study.

The information will be provided to patient verbally and via the patient information sheet (PIS) which will be reviewed and approved by the Regional Ethics Committee (REC) and in accordance with GCP. Contact details for the study team will be provided. Patients will have the opportunity to ask any and all questions during and after the discussion before giving written consent.

The Chief Investigator (CI) will be jointly responsible for obtaining informed consent of all participants according to the approved protocol, principles of Good Clinical Practice and Declaration of Helsinki.

No trial procedure will be undertaken before informed consent is given. Data from procedures performed as part of routine care will not be collected before informed consent is given.

Should a patient lose capacity during the study attempts will be made to replace the patient in the recruitment total but data will be retained. In such an event, the results of symptom questionnaires and diet sheets will be recorded but not used in the final analysis.

Should a patient require re-consenting due to a significant alteration to the trial protocol or new information regarding the study, the IMP or the condition become available it is the joint responsibility of the PI and CI to inform the participants in a timely manner.

The geographical location of the study site is such that most participants are likely to be elderly, frainer Trust and English speaking. The PI and CI take joint responsibility for ensuring the safety of such vulnerable patients and ensuring that they give valid consent free from coercion. Patients with cognitive impairment are eligible as long as they are deemed to be able to give valid consent. Patients who are unable to read the provided PIS for whatever reason can invite a family member or member of the study team to read it to them. If a participant is unable to sign the consent form this may be done by a witness who is not a member of the study team. If a patient is able to produce a legible signature but unable to complete the date the consent form may be dated by a member of the study team.

There will be no PIS or consent forms *printed* in foreign languages as the proportion of patients who require a non-English PIS will be low: 94% of people resident in Yorkshire and the Humber region are English speaking – this will represent 38 of our planned recruitment of 40 patients, however may be more if the recruitment target is extended.

# 7.3 The randomisation scheme

Randomisation will be simple randomisation via a web-based system.

# 7.3.1 Method of implementing the allocation sequence

Randomisation will be performed by the Simple Randomisation Service offered by Sealed Envelope TM (https://www.sealedenvelope.com). Patients will be randomised 1:1 to either A – acetazolamide or B – standard of care in a random permuted block of up to 50 patients (maximum recruitment). Randomisation will be accessed by the study doctors and the sponsors but randomisation will be performed by the study doctors at the point of consent. Sealed Envelope confirms allocation via email to the person performing the randomisation, a copy of which will also be sent to a member of the Research and Development team who will print the email and include in the CRF. The CI ([name]) can be contacted in an emergency via phone.

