# 7.4 Blinding

The trial will be an open label investigation without blinding for two reasons 1) we aim to collect pilot data to inform a larger blinded study 2) the primary endpoints and most secondary endpoints will not be susceptible to bias from unblinded treatment such as urine volumes and serum and urine electrolytes.

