# Serum chloride concentrations

Low serum chloride is associated with adverse outcome in patients with HF. We estimate a clinically meaningful change in chloride to be -0.9 mmol/L per day over the course of an admission (9 days) and -3.6 mmol/L over the four day period of our study (appendix 7). To detect such a difference with 80% power and 5% two-tailed significant with the above anticipated drop out rate we would need to recruit a minimum of 14 patients in the control arm and 17 patients in the ACZ arm.

We expect two potential confounding factors for the co-primary endpoints: 1) daily salt intake and 2) loss of IV access reducing the amount of IV furosemide given. We will collect data on both potential confounders using a daily dietary sheet (on which the patient will record their meals for the day and from which the daily salt intake will be estimated) and recording the "number of hours of furosemide" per day. We do not expect any patient to have excessive salt intake (defined by the European Society of Cardiology Heart Failure Guidelines 2021 as >5g per day). Any patient with >5g salt intake per day or <20 hours of furosemide per day will be removed from the analysis. Due to the exploratory nature of the study we will conduct an intention to treat analysis and a per-protocol analysis in which only patients who completed the study without deviating from the protocol will be included. Thus, we will recruit a maximum of 50 patients – 23 in the control arm and 27 in the ACZ arm with anticipated drop out of 10% and 20% respectively. The extra patients recruited will also act as a contingency should any patient need to be removed from the analyses for reasons of excess salt intake, prolonged loss of IV access, or for the per-protocol analysis.

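### Sections 7.3, 7.3.1 and 10.1 describe three incompatible allocation schemes; the printed 1:1 block of 50 rules out the planned 23/27 split and makes late allocations partly predictable if recruitment nears 50

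*Protocol*

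**What the plan says.** Protocol section 7.3 gives the scheme in one sentence: "Randomisation will be simple randomisation via a web-based system". Section 7.3.1 then says "Patients will be randomised 1:1 to either A – acetazolamide or B – standard of care", and places this "in a random permuted block of up to 50 patients (maximum recruitment". In section 10.1, under serum chloride, the sample size text concludes that "we will recruit a maximum of 50 patients – 23 in the control arm and 27 in the ACZ arm", with drop-out of 10% and 20% respectively.

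On who holds the information, section 7.1.1 says "confirmation of eligibility will be done by the study team". Section 7.3.1 says "randomisation will be performed by the study doctors at the point of consent" and "Sealed Envelope confirms allocation via email to the person performing the randomisation", with a copy to the Research and Development team. Section 7.4 says "The trial will be an open label investigation without blinding". Section 7.1 sets a minimum of 40 and a maximum of 50 patients, and the trial summary gives 40 as the planned size.

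**The concern.** There are two separate problems.

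**Consistency.** Simple randomisation has no block. A 1:1 block has no unequal target. A 23/27 split is an unequal target. Nothing in the protocol reconciles the three, so whoever sets up the list cannot tell which to implement, and the arm sizes quoted at maximum recruitment are not those that section 7.3.1 would produce.

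**Concealment.** In a single 1:1 block of known length, the number of places left in each arm follows from the allocations already made. Here the enrolling doctors know the ratio and the block length from the protocol, and the trial is open label. Some discretion at entry also exists: severe infection is a matter of investigator opinion (section 6), and a patient who fails screening may be re-screened up to three times at 48-hour intervals (section 7.1.2). A doctor who can anticipate the next arm could, even unconsciously, let that influence whether a borderline patient is enrolled. Section 7.4 defends the open-label design on the ground that the endpoints resist bias; that is an argument about measurement and does not cover selection at entry.

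**Working it through.** **Inputs.** Ratio 1:1 and block length 50 (section 7.3.1); 23/27 at 50 patients, with drop-out of 10% control and 20% acetazolamide (section 10.1); recruitment of 40 to 50 (section 7.1); two-sided 5% significance (section 10.1). Power is evaluated at a difference of one SD, which lies within the protocol's ranges (500–1000 mL for both the difference and the SD).

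**1. Where 23/27 comes from.** Splitting 50 in proportion to 1/(1 − 0.10) and 1/(1 − 0.20) gives a control share of 50 × 0.8/(0.8 + 0.9) = 50 × 0.8/1.7 = 23.5, and 26.5 for acetazolamide. The protocol's figure therefore reproduces, as an unequal target adjusted for drop-out. A 1:1 scheme does not aim at it.

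**2. What each scheme gives at 50.**

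| Scheme | Arms at 50 | Probability of 23 control / 27 acetazolamide |
|---|---|---|
| One 1:1 block of 50 | exactly 25/25 | 0 |
| Simple randomisation | Binomial(50, ½) | C(50,23)/2^50 = 9.6% |

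**3. Evaluable patients and power** (two-sample t test, noncentral t).
- 23/27: 23 × 0.9 = 20.7 and 27 × 0.8 = 21.6; power 88.7%.
- 25/25: 25 × 0.9 = 22.5 and 25 × 0.8 = 20.0; power 88.8%.

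**4. Predictability if the block of 50 is filled.** The strategy is to guess the arm with more places left.
- Expected correct guesses above chance: (2^50/C(50,25) − 1)/2 = 3.95. The total is 25 + 3.95 = 28.95 of 50, or 57.9%.
- Over patients 41–50 the rate is 70.0%; over patients 46–50 it is 77.0%.
- The last k allocations are all certain with probability 2·C(50 − k, 25)/C(50, 25): 100% for k = 1, 49% for k = 2, 23% for k = 3, 11% for k = 4. Summing over k gives an expected 1.92 certain allocations.

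**5. Predictability if recruitment stops at 40.** Correct guesses are 21.95 of 40, or 54.9%; over patients 31–40 the rate is about 59%. The chance that any allocation is certain is about 0.02%.

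**6. A longer list.** With a 1:1 list of 100 stopped at 50, the same strategy is right 52.2% of the time overall and 53.6% over the last ten. The size of one arm has SD √(50 × ¼ × 50/99) = 2.5 and a 95% range of 20 to 30. Exactly 25/25 occurs with probability C(50,25)²/C(100,50) = 16%. Even fully simple randomisation of 50 gives average power of 88.1%, a loss of 0.7 points from 88.8%.

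**7. Short fixed blocks, for comparison.** A known block of 4 over 50 patients gives about 35 correct guesses and 16 certain allocations, which is worse than the present scheme.

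**The case against.** The case for leaving the scheme alone has several parts.

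- **The wording may be partly a product name.** Section 7.3.1 names the vendor's offering as a simple randomisation service, and section 7.3 may only echo that. This is plausible, but it leaves 7.3.1 and 10.1 in conflict and makes the block the operative scheme.
- **Predictability depends on recruitment nearing 50.** This stands. The planned size is 40, and at 40 the advantage from guessing is small. The protocol does try to replace patients in several situations (sections 7.2, 7.8, 7.9, 8.1, 9.9 and 10.7), but section 10.1 calls the extra patients a contingency and section 10.7 expects missing data to be minor. For illustration only: if recruitment continued until 40 patients had completed, with average drop-out of 15%, it would reach 40/0.85 = 47, and guessing would be right about 64% of the time for patients 41–47.
- **Entry is constrained.** Treating clinicians decide on the need for intravenous diuretic, and many exclusions are laboratory or blood-pressure thresholds. This narrows the route to selection bias without closing it. That each doctor sees every allocation is an inference from the open-label setting and a small team; the email goes only to the person randomising and to Research and Development.
- **The arm sizes have no consequence for power.** This is correct; the mismatch is an error of statement.

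A reader might go further and infer that allocation is predictable throughout, that 23/27 could never arise, or that the chloride minimum of 14 and 17 leaves the trial short under 1:1. The document supports none of these. Predictability is concentrated at the end of a filled block. Under literal simple randomisation nothing is predictable and 23/27 can arise by chance. The chloride minimum is overtaken by the minimum recruitment of 40. Nor does any section say that a replacement takes the arm of the patient replaced.

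**Conclusion.** The inconsistency is definite: sections 7.3, 7.3.1 and 10.1 cannot all be followed, and under the 1:1 block of 50 the arms at 50 are 25/25. Correcting the arm sizes changes power by about 0.1 points at a difference of one SD.

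The concealment weakness is real but conditional. It assumes that the block is a single one of 50, that the study doctors know past allocations, and that recruitment approaches the maximum. On those assumptions about 70% of guesses for patients 41–50 are right and about two allocations are certain. At the planned 40 it is about 55% overall with almost none certain. These figures show how far allocations can be guessed; they do not show that any biased selection would occur. The change is worth making because the contradiction has to be corrected anyway and the added cost is minor.

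**What to change.** 1. State one 1:1 method, in the same terms, in sections 7.3 and 7.3.1.
2. Delete the block length from the protocol. Have the existing web service hold a 1:1 list longer than maximum recruitment (100 entries, for example), with its length and any blocking withheld from the study doctors. Do not substitute short fixed blocks, which are easier to guess.
3. In section 10.1, replace 23/27 with an expected 25 per arm at 50, leaving about 22 control and 20 acetazolamide patients evaluable after 10% and 20% drop-out. Describe 25 as expected, not guaranteed: a 100-entry list stopped at 50 gives exactly 25/25 only 16% of the time.

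The cost is a protocol wording change and one regenerated list. Balance becomes slightly looser (arm size SD about 2.5, range about 20 to 30), with less than one percentage point of average power lost.

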# 7.4 Blinding

The trial will be an open label investigation without blinding for two reasons 1) we aim to collect pilot data to inform a larger blinded study 2) the primary endpoints and most secondary endpoints will not be susceptible to bias from unblinded treatment such as urine volumes and serum and urine electrolytes.

# 7.5 Unblinding

No unblinding required.

# 7.6 Baseline data

- Medical history including age (years), sex, co-morbidities, and aetiology of heart failure
- Bedside observations including body weight, systolic and diastolic blood pressure, heart rate and rhythm.
- Patient symptoms including: investigator assessed New York Heart Association class, peripheral oedema severity (none = 0, trace = 1, ankles = 2, below knees = 3, above knees = 4, sacral = 5), pulmonary congestion severity (lung crackles) (absent = 0, bibasal = 1, midzone = 2, whole lung = 3), jugular venous pressure severity (not visible = 0, 1-4cm above the sternal notch = 1, >4cm above the sternal notch = 2, up to the earlobes = 3), patient assessed symptoms using the Likert breathlessness scale (patients will be asked to rate their breathlessness severity on a 5-point scale of: 1=not short of breath, 2=mildly short of breath, 3=moderately short of breath, 4=severely short of breath, 5=very severely short of breath)

- Echocardiographic data including: left ventricular ejection fraction either calculated by SimpsonSHS Trust biplane method or qualitatively on transthoracic echocardiogram performed either as routine practice or by the investigator, presence of moderate or worse valve disease, inferior vena cava diameter
- Biochemical data including: NTproBNP, haemoglobin (g/dL), haematocrit (fraction), sodium (mmol/L), chloride (mmol/L), potassium (mmol/L), bicarbonate (mmol/L), creatinine (µmol/L), urea (mmol/L).
- Data on pre-admission medical and device therapy including: angiotensin converting enzyme inhibitor, angiotensin receptor blocker, sacubitril valsartan, beta-blocker, mineralocorticoid receptor antagonist, oral loop diuretic dose, presence of cardiac resynchronisation therapy device, presence of implantable cardioverter defibrillator, cumulative dose of in-patient loop diuretic (mg / day)

